## 13. LIST OF TABLES AND DATA LISTINGS

### 13.1 Statistical Tables

The statistical tables are to be generated using SAS version 9.4. In general, the sample size (n) is to be presented by whole number; minimum, and maximum are to be presented based on the number of decimal points of the reported value and other parameters with one more decimal point. The count will be the whole number. The percentage will be presented to one decimal place.

Number	Title	Population
14.1.1	Patients Disposition	All
14.1.2.1	Patients Demographics Overall, by Gender and by ADA status	Safety
14.1.2.2	Patients Demographics by Fabry Disease Classification and by Previous ERT	Safety
14.1.2.3	Patients Demographics by eGFR and by Use of ACEi/ARB	Safety
14.1.3.1	Baseline Characteristics Overall, by Gender and by ADA status	Safety
14.1.3.2	Baseline Characteristics by Fabry Disease Classification and by Previous ERT	Safety
14.1.3.3	Baseline Characteristics by eGFR and by Use of ACEi/ARB	Safety
14.1.4.1	Fabry Disease Medical History Overall, by Gender and by ADA status	Safety
14.1.4.2	Fabry Disease Medical History by Fabry Disease Classification and by Previous ERT	Safety
14.1.4.3	Fabry Disease Medical History by eGFR and by Use of ACEi/ARB	Safety
14.1.5.1	Other Medical History Overall, by Gender and by ADA status	Safety
14.1.5.2	Other Medical History by Fabry Disease Classification and by Previous ERT	Safety
14.1.5.3	Other Medical History by eGFR and by Use of ACEi/ARB	Safety
14.1.6	Treatment Compliance	Efficacy
14.2.1.1	Kidney Functions - eGFR Summary – Overall and by Gender	Efficacy
14.2.1.2	Kidney Functions – Shift in eGFR Categories from Baseline to Week 52 or Early Discontinuation	Efficacy
14.2.1.3.1	Kidney Functions (eGFR Slope) Overall, by Gender and by ADA status	Efficacy
14.2.1.3.2	Kidney Functions (eGFR Slope) by FD Classification and by Previous ERT	Efficacy
14.2.1.3.3	Kidney Functions (eGFR Slope) by eGFR and by Use of ACEi/ARB	Efficacy
14.2.2.1.1	Plasma Lyso-Gb3 Concentrations Overall, by Gender and by ADA status	Efficacy
14.2.2.1.2	Plasma Lyso-Gb3 Concentrations by FD Classification and previous ERT	Efficacy
14.2.2.2.1	Plasma Lyso-Gb3 Concentrations – Deterioration Compared to Baseline Overall, by Gender and by ADA Status	Efficacy
14.2.2.2.2	Plasma Lyso-Gb3 Concentrations - Deterioration Compared to Baseline by FD Classification and previous ERT	Efficacy
14.2.3	Plasma Gb3 Concentrations Overall and by Gender	Efficacy
14.2.4	Urine Lyso-Gb3 Concentrations Overall and by Gender	Efficacy

14.2.5.1	UPCR Categories Overall, by Gender and by ADA Status	Efficacy
14.2.5.2	UPCR Categories or by FD classification and by Previous ERT	Efficacy
14.2.5.3	UPCR Categories by Usage of ACEi/ARB	Efficacy
14.2.5.4	UPCR - Shift from Baseline to Week 52 or Early Discontinuation	Efficacy
14.2.5.5	UPCR - Shift from Baseline to Week 52 or Early Discontinuation by usage of ACEi/ARB	Efficacy
14.2.6	Echocardiogram Qualitative Assessments – Shift from Baseline	Efficacy
14.2.7.1	Number of Subjects Used Pain Medications at Any Time During the Study	Efficacy
14.2.7.2	Number of Different Pain Medications That a Subject Received During the Study	Efficacy
14.2.7.3	Pain Medication Use – Shift from Baseline to Last Visit	Efficacy
14.2.7.4	Pain Medication Use – Shift from Baseline to Last Visit by FD Classification	Efficacy
14.2.7.5	Pain Medication Use – Shift from Baseline to Last Visit by Previous ERT	Efficacy
14.2.8.1	Stress Test Quantitative Assessments	Efficacy
14.2.8.2	Stress Test Overall Impression - Shift from Baseline	Efficacy
14.2.9.1	Short Form Brief Pain Inventory (BPI) Severity Domains	Efficacy
14.2.9.2.1	Short Form Brief Pain Inventory (BPI)- Average Pain Over the Last 24 Hours by Gender and ADA Status	Efficacy
14.2.9.2.2	Short Form Brief Pain Inventory (BPI)- Average Pain Over the Last 24 Hours by FD Classification and by Previous ERT and by ADA Status	Efficacy
14.2.9.2.3	Short Form Brief Pain Inventory (BPI) - Average Pain Severity Improvement or No Change Compared to Baseline	Efficacy
14.2.9.3	Short Form Brief Pain Inventory (BPI) Interference Domains	Efficacy
14.2.10.1	Mainz Severity Score Index (MSSI)	Efficacy
14.2.10.2	Mainz Severity Score Index (MSSI) Overall Score - Shift from Baseline	Efficacy
14.2.11.1	Quality of Life EQ-5D-5L - Overall Health Score	Efficacy
14.2.11.2	Quality of Life EQ-5D-5L Qualitative Assessments	Efficacy
14.2.12	Number of Subjects with Fabry Clinical Events	Efficacy
14.3.1.1	Exposure Overall, by Gender and by ADA status	Safety
14.3.1.2	Exposure by FD Classification and by Previous ERT	Safety
14.3.1.3	Exposure by eGFR and by Use of ACEi/ARB	Safety
14.3.2.1	Number of Infusions Administered at Home, on Site and Overall	Safety
14.3.2.2	Infusions Duration (hours) Overall and By Patient Weight	Safety
14.3.3.1.1	Summary of TEAE	Safety
14.3.3.1.2	Summary of TEAE by Gender by ADA Status	Safety
14.3.3.1.3	Summary of TEAE by FD Classification and by Previous ERT	Safety
14.3.3.2	Summary of Injection Site Reaction	Safety
14.3.3.3.1	TEAE by MedDRA SOC and PT	Safety
14.3.3.3.2	TEAE by MedDRA SOC and PT and Severity	Safety
14.3.3.3.3	TEAE by MedDRA SOC, PT and Relationship to Study Drug	Safety
14.3.3.4.1	Serious TEAE by MedDRA SOC and PT	Safety
14.3.3.4.2	Serious TEAE by MedDRA SOC, PT and Relationship to Study Drug	Safety
14.3.3.5.1	Summary of IRR by Overall and by Location of Administration	Safety

14.3.3.5.2	Summary of IRR by Gender and by ADA	Safety
14.3.3.5.3	Summary of IRR by FD Classification and by Previous ERT	Safety
14.3.3.6.1	IRR by MedDRA SOC and PT	Safety
14.3.3.6.2	IRR by MedDRA SOC, PT and Severity	Safety
14.3.4.1	Anti-Drug Antibodies	Safety
14.3.4.2	ADA Status - Shift from Baseline	Safety
14.3.5	Vital Signs	Safety
14.3.6.1	Laboratory Test Results – Biochemistry	Safety
14.3.6.2	Laboratory Test Results – Hematology	Safety
14.3.6.3	Laboratory Test Results – Urinalysis	Safety
14.3.6.4	Laboratory Test Results – Coagulation Profile at Screening	Safety
14.3.6.5	Laboratory Test Results – Vitamin D at Screening	Safety
14.3.7	Physical Examinations	Safety
14.3.8.1	Electrocardiography (ECG) Quantitative Parameters	Safety
14.3.8.2	Electrocardiography (ECG) Qualitative Parameters	Safety
14.3.9.1	Prior and Concomitant Medications	Safety
14.3.9.2	Subjects Treated with ACEi and/or ARBs	Safety
14.3.9.3.1	Infusion Premedication	Safety
14.3.9.3.2	Shift from Baseline to Last Visit in the Number of Infusion Premedication	Safety

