10.2 Subject Populations

10.2.1 Intent-to-Treat (ITT) Population

Intent-to-treat (ITT) population is defined as patients who received at least one complete dose of study medication.

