## 5. ANALYSIS POPULATIONS (ANALYSIS SETS)

### 5.1 Safety Population

The safety population consists of all subjects who received at least one dose (partial or complete) of pegunigalsidase alfa in the study. All safety analyses will be based on this population.

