### 5.2 Efficacy Population

The efficacy population consists of all subjects who received any dose of pegunigalsidase alfa 2 mg/kg in the study and who have at least one post-baseline visit with an efficacy evaluation. All efficacy analyses will be based on this population.

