## 9. ANALYSIS OF EFFICACY ENDPOINTS

All the analyses presented in this section will be done using the efficacy population. This study is descriptive in nature and sample size is not based on statistical ground.

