### **9.13      Fabry Clinical Events**

Fabry clinical events (FCE) are classified into four categories: renal, cardiac, cerebrovascular and non-cardiac death. The adjudicated decisions will be made by the Sponsor medical monitor, based on reported adverse events and clinical information included in the data base.

The criteria for FCE are the following and based on Hopkin (2016):

1. Renal events:

- First occurrence of either initiation or chronic dialysis ( $>40$  days),

- Renal transplantation.

2. Cardiac events:

- Cardiac related death,
- Myocardial infarction,
- First time congestive heart failure,
- Atrial fibrillation,
- Ventricular tachycardia,
- Evidence of progressive heart disease severe enough to require pacemaker,
- Implantation of pacemaker,
- Bypass surgery,
- Coronary artery dilatation,
- Implantation of defibrillator.

3. Cerebrovascular events:

- Hemorrhagic or ischemic stroke,
- Transient Ischemic Attack.

4. Non-cardiac related Death.

The number and percentage of patients with FCE (regardless of type of event) and by type will be presented. For the number of FCE (regardless of type of event) patients who had more than one type will be counted once.

FCE listing will show the categories by SOC and PT and the time to event measured from Visit 1.

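### Fabry clinical events, deaths included, are tabulated on a population that needs a post-baseline efficacy evaluation, so a patient lost to an early event can drop out of the count

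*SAP*

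**What the plan says.** SAP Section 9 fixes one population for everything in it: "All the analyses presented in this section will be done using the efficacy population". Section 9.13, on Fabry clinical events, falls under that rule and makes no exception. The table list in Section 13.1 agrees, giving Efficacy as the population for Table 14.2.12, "Number of Subjects with Fabry Clinical Events".

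Section 5.2 defines that population as patients who received any 2 mg/kg dose and "who have at least one post-baseline visit with an efficacy evaluation". It does not define an efficacy evaluation. The Safety population in Section 5.1 has no such condition: "The safety population consists of all subjects who received at least one dose (partial or complete) of pegunigalsidase alfa in the study".

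On the endpoint itself, Section 9.13 states: "Fabry clinical events (FCE) are classified into four categories: renal, cardiac, cerebrovascular and non-cardiac death". Cardiac death is listed separately within the cardiac category. The sponsor's medical monitor adjudicates, "based on reported adverse events and clinical information included in the data base". The planned output is simple: "The number and percentage of patients with FCE (regardless of type of event) and by type will be presented".

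The protocol's Intent-to-Treat set (Section 10.2.1) was "patients who received at least one complete dose of study medication", with no post-baseline condition. SAP Section 12 discloses that the post-baseline condition was added and, as a separate item, that Fabry clinical events were added as an endpoint. It does not discuss how the two interact.

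**The concern.** A post-baseline requirement is reasonable for change-from-baseline endpoints, because without a later value there is nothing to analyse. It does not suit an endpoint that includes death. Here the event being counted can be the reason a patient fails the membership condition, so inclusion in the table can depend on the outcome.

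The condition also serves no purpose for this endpoint. Adverse event data exist for every treated patient from the first infusion, so an event can be adjudicated whether or not a creatinine or any other efficacy measure was obtained afterwards.

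At stake is the count and percentage in one table. With 30 patients, one lost event is enough to turn a non-zero proportion into zero. The report could also become internally inconsistent, with the all-subject listing of Fabry clinical events showing a death that the matching summary table omits.

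**Working it through.** The documents give no Fabry event rate and no power calculation, so there is no planned figure to reproduce. The check traces the definitions and then sizes the effect on assumed counts.

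**1. When can a patient first qualify?**
- Protocol Section 9.2.3 (Week 2) lists antibodies only, which the SAP treats as a safety endpoint.
- Protocol Section 9.2.4 (Visit 2, Week 4 ± 3 days) has the first post-baseline serum creatinine, hence the first eGFR.
- The exposed window is therefore about 28 of 52 × 7 = 364 days: 28/364 = 7.7% of planned follow-up.
- The protocol flow chart also appears to mark a medication review at Week 2; the SAP's copy starts it at Visit 2. If that review were accepted as an evaluation of pain medication use, the window would shrink to about 14/364 = 3.8%.

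**2. Does anything restore an excluded patient?**
- SAP Section 7.2 imputes only adverse event and medication items and makes no other imputation for safety or efficacy endpoints.
- Section 9.13 has no add-back rule.
- Section 13.1 plans no Fabry event table on the Safety population.

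**3. Effect on the table.** Take N = 30 treated (SAP Section 4.1), x patients with an event, and e of them lost because of it. The Safety set gives x/30; the Efficacy set gives (x − e)/(30 − e). The counts are assumed. The exact (Clopper-Pearson) 95% limits are added here for scale only; Section 9.13 plans no interval.

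| Patients with event | Lost early | Safety set | Efficacy set |
|---|---|---|---|
| 1 | 1 | 1/30 = 3.3% (0.1–17.2) | 0/29 = 0.0% (0.0–11.9) |
| 2 | 1 | 2/30 = 6.7% (0.8–22.1) | 1/29 = 3.4% (0.1–17.8) |
| 3 | 1 | 3/30 = 10.0% (2.1–26.5) | 2/29 = 6.9% (0.8–22.8) |

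For the zero count, the upper limit is 1 − 0.025^(1/29) = 11.9%.

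**4. Effect of dropping an event-free patient.** If one patient leaves early without an event and another has an event later, the table shows 1/29 = 3.4% instead of 1/30 = 3.3%. This error runs the other way and is much smaller.

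**5. How likely is an event-driven loss?** Assume a constant annual event risk r, with a share s of early events preventing any later evaluation. The four-week risk is p = 1 − (1 − r)^(4/52), and the chance of at least one such patient among 30 is 1 − (1 − s·p)^30.

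| Assumed r | p | s = 10% | s = 50% |
|---|---|---|---|
| 2% | 0.00155 | 0.5% | 2.3% |
| 5% | 0.00394 | 1.2% | 5.7% |
| 10% | 0.00807 | 2.4% | 11.4% |

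Both r and s are assumptions; the documents give neither.

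**The case against.** Three stronger readings are tempting, and the documents do not support them.

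- **A reader might infer that any early event removes the patient.** It does not. Section 5.2 has no event-free condition. A patient with an early infarction, stroke or arrhythmia who attends Visit 2 and has a creatinine stays in the set and is counted. Protocol Sections 6.3.3 and 9.2.9 also ask sites to attempt continued follow-up and the Visit 14 tests after discontinuation. What remains is early death, or departure with no later efficacy evaluation.
- **A reader might infer that the bias can only lower the rate.** That holds only for exclusions caused by an event. Dropping early leavers without an event raises the rate slightly, so the net direction depends on who is excluded.
- **A reader might infer that a death could be hidden.** It could not. Serious and fatal treatment-emergent events are summarised on the Safety set (Sections 10 and 10.2.1), and events leading to withdrawal or death are presented by patient. Listing 16.2.8 gives Fabry events, and the listings cover all subjects (Section 13.3). The disposition table reports the size of each analysis set (Section 8.1).

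It can also be argued that Fabry clinical events are themselves a listed efficacy endpoint (Section 3.2.2), so an adjudicated event might count as an efficacy evaluation. The SAP does not settle this. Exclusion is the natural reading of a condition that speaks of a visit, but it is not certain.

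Finally, the table is exploratory, no tests are planned (Section 7.4), and the chance of an affected patient is low. All of this stands, and it limits how serious the point is. It gives no reason to keep a condition that the endpoint does not need and that can fail when an early death occurs.

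**Conclusion.** The point holds in a limited form. On the natural reading of Section 5.2, a patient who dies, or leaves with no later efficacy evaluation, because of a Fabry clinical event before about Week 4 is missing from both parts of the proportion in Table 14.2.12. The adjudication itself needs no efficacy visit.

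One such patient among 30 moves the reported figure by 3.3 percentage points at most in the cases shown, from 1/30 to 0/29. Under the assumed risks, the chance of at least one such patient is roughly 0.5% to 11%. If all 30 treated patients have a post-baseline efficacy evaluation, the effect is nil; the documents do not say whether they do.

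Severity is minor: one exploratory, descriptive table is affected, with no consequence for type I error or power, and the event stays visible elsewhere in the report.

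**What to change.** In SAP Section 13.1, change the population of Table 14.2.12 from Efficacy to Safety. In Section 9.13, add one sentence stating that, as an exception to the general rule of Section 9, Fabry clinical events are summarised in all patients who received any infusion, partial or complete. A line in Section 12 would record the choice.

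Declaring instead that an adjudicated event counts as an efficacy evaluation would be a weaker repair. It would bring back patients with an event but still drop event-free early leavers, so membership would still depend on the outcome.

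The cost is one word and one sentence, with no new data, patients or procedures. It is a free improvement.

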## 13.2 Figures

Number	Title	Population
15.2.1.1	Spaghetti Plot of eGFR over Time	Efficacy
15.2.1.2	Mean eGFR +/-SE Over Time	Efficacy
15.2.1.3	eGFR Slopes - Boxplots for Subgroups	Efficacy
15.2.2.1	Spaghetti Plot of Plasma Lyso-Gb3 Concentrations over Time (Male Subjects)	Efficacy
15.2.2.2	Spaghetti Plot of Plasma Lyso-Gb3 Concentrations over Time (Female Subjects)	Efficacy
15.2.2.3	Mean Plasma Lyso Gb3 +/-SE Over Time	Efficacy
15.2.2.4	Plasma Lyso Gb3 Change from Baseline - Boxplots for Subgroups	Efficacy

### 13.3 Data Listings

Data listings will be show first treated patients followed by screen failures, and within these two groups, it will be sorted by subject ID. The listings will present all data collected, for all subjects.

Number	Title
16.1.1	Subject Disposition
16.1.2	Protocol Deviations
16.1.3	Subjects Demographics
16.1.4	Fabry Disease Medical History
16.1.5	Other Medical History
16.1.6	Treatment Compliance
16.1.7	Body Measurements
16.2.1	Kidney Functions (eGFR and eGFR Slope)
16.2.2	Gb3 Concentration (Plasma GB3, Plasma Lyso-Gb3 and Urine Lyso-Gb3) including Change from Baseline
16.2.3	Echocardiogram
16.2.4	Stress Test
16.2.5	Brief Pain Inventory (BPI)
16.2.6	Mainz Severity Score Index (MSSI)
16.2.7	Quality of Life EQ-5D-5L
16.2.8	Fabry Clinical Events
16.3.1	Exposure
16.3.2.1	Pre-treatment Adverse Events
16.3.2.2	Treatment Emergent Adverse Events
16.3.2.3	Treatment-Emergent Adverse Events Leading to Withdrawal or Death
16.3.2.4	Infusion Related Reactions
16.3.3	Vital Signs
16.3.4.1.1	Laboratory – Anti Drug Antibodies: IgG for PRX-102
16.3.4.1.2	Laboratory: Anti-Drug Antibodies: IgG for Agalsidase Beta
16.3.4.1.3	Laboratory: Anti-Drug Antibodies: IgG for Agalsidase Alfa
16.3.4.1.4	Laboratory: Anti-Drug Antibodies: IgE
16.3.4.2	Laboratory– Hematology
16.3.4.3	Laboratory– Coagulation Profile
16.3.4.4	Laboratory– Vitamin D
16.3.4.5	Laboratory– Urinalysis (Dipstick)
16.3.4.6	Laboratory– Biochemistry, Serum Creatinine and Cystatin C
16.3.4.7	Laboratory– Spot Urine
16.3.4.8	Laboratory– Serology
16.3.4.9	Laboratory: Pregnancy
16.3.5	Physical Examination
16.3.6	Electrocardiography (ECG)
16.3.7.1	Prior and Concomitant Medications
16.3.7.2	Infusion Premedication During Study

16.3.8	Chest X-rays
16.3.9	Brain MRI
16.3.10	PK Concentrations

## 14. SHELLS

Tables and listings shells will be provided in a separate document and provide a framework of the statistical analysis for the study and final shells may be slightly different in appearance. As long as the same information is presented, this is considered to be in alignment with the shells below.

